## 7.6. Treatment Compliance

When subjects are dosed at the study site, they will receive study treatment under medical supervision by the Investigator or designee. The dose of study treatment and study subject identification will be confirmed at the time of dosing by a member of the study site staff other than the person responsible for study treatment accountability.

When subjects self-administer study treatment at home, the Investigator or designee will assess compliance with study treatment by counting the remained doses of FF/UMEC/VI in ELLIPTA as appropriate at the clinic visits and by querying the subject during the clinic visits as necessary, and document it in the source documents and CRF. A record of the number of the investigational product dispensed to and taken by each subject must be maintained and reconciled with study treatment and compliance records by the person responsible for study treatment accountability. Treatment start and stop dates will also be recorded in the CRF. Subjects should be  $\geq 80\%$  to  $\leq 120\%$  compliant on taking study treatment between each pair of scheduled and consecutive on-treatment clinic visits.

Subjects who fall outside this range should be re-educated on treatment compliance by their site. The Investigator should document this re-education in the source documents.

If the study treatment is withdrawn early or a subject is unable comply with the study treatment method and repeatedly falls outside the acceptable compliance range, the sponsor/monitor should be notified of it for discussion about appropriateness of continuation of the study in the subject.

## **7.7. Concomitant Therapy**

Any medication or vaccine (including over-the-counter or prescription medicines, vitamins, and/or herbal supplements) that the participant is receiving at the time of enrollment or receives during the treatment period must be recorded along with:

- reason for use
- dates of administration including start and end dates
- dosage information including dose and frequency

All asthma medications used within approximately 4 weeks prior to screening should also be recorded in the CRF. Medications initiated after completion of the assessments at Visit 7/EOT or the Early Withdrawal Visit will not be recorded in the CRF unless taken to treat an AE or asthma exacerbation. Concomitant medications relating to a SAE need to be entered on the CRF, if SAE is occurred from informed consent until the initiation of treatment period.

The Medical Monitor should be contacted if there are any questions regarding concomitant or prior therapy.

Detailed information of permitted and prohibited medications is included in the SRM. Participants who have completed the Visit 7/EOT or Early Withdrawal Visit are allowed to use any medications prescribed by the Investigator or primary care physician.

### **7.7.1. Prohibited Concomitant Medications**

Use of the medications listed in [Table 6](#) is not permitted during the study.

**Table 6 Concomitant Medications (○: permitted, X: prohibited)**

Medication	Prior to Visit 1	Run-in period	Treatment period	Follow-up period
Inhaled short-acting anticholinergics	Prohibited within 6 hours	X	X	○
Inhaled short-acting anticholinergics + short-acting $\beta_2$ agonist combination	Prohibited within 6 hours	X	X	○
Inhaled long-acting anticholinergics	○	○ 	X	○
Immunosuppressive medications including immunomodulators	Prohibited within 12 weeks	X	X	○
Inhaled LABA (e.g., salmeterol, formoterol, indacaterol, olodaterol) or combination products containing inhaled LABA (e.g., Adoaire, Symbicort)	○	○ 	X	○
Non-Inhaled LABA (e.g., Hokunalin Tape)	Prohibited within 24 hours	X	X	○
Inhaled short-acting beta 2 -agonist (rescue salbutamol will be provided and is permitted during the study)	Prohibited within 6 hours	X	X	○
ICS	○	○ 	X	○
Theophyllines, slow-release bronchodilators, ketotifen, nedocromil sodium, sodium cromoglycate, roflumilast	Prohibited within 48 hours	X	X	○
Medicinal marijuana 	Prohibited within 6 months	X	X	X
Other investigational products	Within 30 days or within 5 drug half-lives of the investigational drug (whichever is longer)	X	X	X

1. Start of use is prohibited.
2. Use of inhaled medicinal cannabis is prohibited. Use of medicinal cannabis by any other route of administration is also prohibited unless written approval is obtained from the Medical Monitor prior to Visit 1.

## 7.7.2. Permitted Concomitant Medications

### 7.7.2.1. Permitted Asthma Medications

In addition to study treatment, the following medications are permitted during this study:

- Systemic corticosteroids ( $\leq 5$  mg/day of prednisolone or equivalent) will be permitted provided that treatment was initiated at least 12 weeks prior to Visit 1, remains stable for the 8 weeks prior to Visit 1 and the subject remains in the maintenance phase throughout the study (the only exception being the treatment of moderate/severe asthma exacerbations [see below]).
- Anti-immunoglobulin E (IgE) (e.g. omalizumab) treatment will be permitted provided that treatment was initiated at least 16 weeks prior to Visit 1 and the subject remains in the maintenance phase throughout the study.
- Anti-interleukin (IL)-5 (e.g. mepolizumab) treatment will be permitted provided that treatment was initiated at least 16 weeks prior to Visit 1 and the subject remains in the maintenance phase throughout the study.
- Anti-leukotriene treatment will be permitted provided that treatment was initiated at least 12 weeks prior to Visit 1 and the subject remains in the maintenance phase throughout the study.
- Study-provided salbutamol will be dispensed at Visit 1 for use as rescue medication throughout the duration of the study. GSK will not provide any rescue drug to the sites in principle.

Temporary additions of medications are permitted for the treatment of moderate asthma exacerbations at the Investigator's/treating physician's discretion. Asthma exacerbations should be treated in line with national and international recommendations and local medical standards. Asthma medications permitted on a temporary basis to treat a moderate asthma exacerbation include but are not limited to the following (the Medical Monitor may be contacted for additional guidance, see the Medical Monitor/Sponsor Information Page):

- An increase in ICS dose
- Systemic corticosteroids (tablets, suspension or injection) (or an increase in systemic corticosteroid dose for those subjects receiving maintenance systemic corticosteroids)
- Change in SABA use (i.e., routinely scheduled versus as needed use)
- Leukotriene receptor antagonists (LTRAs)
- Oral theophylline
- By definition, a severe asthma exacerbation will be treated with systemic corticosteroid (tablets, suspension or injection) for at least 3 consecutive days (or at

least double the existing maintenance dose of systemic corticosteroid, if applicable, for at least 3 consecutive days). See Section [9.5.4.2..](#)

### **7.7.2.2. Permitted Non-Asthma Medications**

The following medications are permitted during this study:

- Medications for rhinitis (e.g., intranasal corticosteroids, antihistamines [including ocular and intranasal], cromolyn, nedocromil, nasal decongestants)
- Antibiotics for short term treatment of acute infections. Long term treatment with topical or ophthalmic antibiotics are permitted.
- Decongestants: Subjects may take decongestants during the study, but these are disallowed for 24 hours prior to ECG measurements.
- Immunotherapy: Immunotherapy for the treatment of allergies is allowed during the study provided it was initiated 4 weeks prior to Visit 1 and subjects remain in the maintenance phase for the duration of the study.
- Topical and ophthalmic corticosteroids
- Systemic and ophthalmic  $\beta$ -blockers: Administer with caution as systemic  $\beta$ -blockers block the pulmonary effect of  $\beta$ -agonists and may produce severe bronchospasm in patients with reversible obstructive airways disease. Cardioselective  $\beta$ -blockers also should be administered with caution.
- Localized corticosteroid injections (e.g. intra-articular and epidural)
- Tricyclic antidepressants and monoamine oxidase inhibitors (MAOIs). Administer with extreme caution as they may potentiate the effects of  $\beta$ -agonists on the cardiovascular system, including QTc prolongation.
- Diuretics. Caution is advised in the co-administration of  $\beta$ -agonists with non-potassium sparing diuretics as this may result in ECG changes and/or hypokalemia.
- Cytochrome P450 3A4 (CYP3A4) inhibitors: Caution should be exercised when considering the coadministration of long-term ketoconazole and other known strong CYP3A4 inhibitors (e.g., ritonavir, clarithromycin, conivaptan, indinavir, itraconazole, lopinavir, nefazodone, neflifavir, saquinavir, telithromycin, troleandomycin, voriconazole) because increased systemic corticosteroid and increased cardiovascular adverse effects may occur.
- Vaccinations (e.g., influenza vaccine, pneumonia vaccine, herpes zoster vaccine). Administration of influenza and pneumonia vaccines should be considered based on clinical discretion of the Investigator and local/national guidelines. Current influenza vaccines and pneumonia vaccines will be captured on the concomitant medication pages of the CRF.)

All medications for other disorders may be continued throughout the study provided their use would not be expected to affect the subjects' lung function or safety assessments (e.g., cardiac measurements). However, no systemic corticosteroids for other conditions will be permitted.

#### **7.7.2.3. Permitted Non-Drug Therapies**

Use of continuous positive airway pressure (CPAP) for treatment of obstructive sleep apnea syndrome will be permitted provided that the treatment was initiated at least 6 weeks prior to the screening visit (Visit 1) and the subject remains on CPAP throughout the study.

### **7.8. Treatment after the End of the Study**

Subjects will not receive any additional treatment from GSK after completion of the study because other treatment options are available.

The Investigator is responsible for ensuring that consideration has been given to the post-study care of the subject's medical condition, whether or not GSK is providing specific post-study treatment.

## **8. DISCONTINUATION CRITERIA**

### **8.1. Discontinuation of Study Treatment**

A subject may be withdrawn from study treatment at any time. A reason for premature discontinuation of study treatment (e.g., AE, lack of efficacy [including acute moderate or severe asthma exacerbation], protocol deviation, Investigator discretion, consent withdrawn) must be captured in the CRF.

A subject must be withdrawn from study treatment if any of the following stopping criteria are met:

- Liver Chemistry: Meets any of the protocol-defined liver chemistry stopping criteria (see Section 8.1.1. and [Appendix 6](#)).
- QTc: Meets any of the protocol-defined stopping criteria (see Section 8.1.2.).
- Pregnancy: Positive pregnancy test (see Section 9.2.7. and [Appendix 4](#))

[figure not shown]
### 8.1.1. Liver Chemistry Stopping Criteria

**Liver chemistry stopping and increased monitoring criteria** have been designed to assure participant safety and evaluate liver event etiology (in alignment with the FDA premarketing clinical liver safety guidance). These protocol guidelines are in alignment with FDA premarketing clinical liver safety guidance:

<http://www.fda.gov/downloads/Drugs/GuidanceComplianceRegulatoryInformation/Guidances/UCM174090.pdf>

[figure not shown]
Discontinuation of study treatment for abnormal liver tests should be considered by the investigator when a participant meets one of the conditions outlined in the algorithm or if the investigator believes that it is in the best interest of the participant.

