### **8.1.3. Temporary Discontinuation**

A subject who discontinues the study treatment must be withdrawn from the study.

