### Collection of Pregnancy Information

#### Female Participants who become pregnant

- Investigator will collect pregnancy information on any female participant, who becomes pregnant while participating in this study.
- Information will be recorded on the appropriate form and submitted to GSK within 24 hours of learning of a participant's pregnancy.
- Participant will be followed to determine the outcome of the pregnancy. The investigator will collect follow up information on participant and neonate, which will be forwarded to GSK. Generally, follow-up will not be required for longer than 6 to 8 weeks beyond the estimated delivery date.
- Any termination of pregnancy will be reported, regardless of fetal status (presence or absence of anomalies) or indication for procedure.
- While pregnancy itself is not considered to be an AE or SAE, any pregnancy complication or elective termination of a pregnancy will be reported as an AE or SAE.
- A spontaneous abortion is always considered to be an SAE and will be reported as such.
- Any SAE occurring as a result of a post-study pregnancy which is considered reasonably related to the study treatment by the investigator, will be reported to GSK as described in [Appendix 3](#). While the investigator is not obligated to actively seek this information in former study participants, he or she may learn of an SAE through spontaneous reporting.

Any female participant who becomes pregnant while participating will discontinue study treatment or be withdrawn from the study.

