## 12.6. Appendix 6: Liver Safety: Required Actions and Follow-up Assessments

Phase III-IV liver chemistry stopping and increased monitoring criteria have been designed to assure participant safety and evaluate liver event.

Liver Chemistry Stopping Criteria - Liver Stopping Event	
ALT-absolute	ALT $\geq$ 8xULN
ALT Increase	ALT $\geq$ 5xULN but $<8$ xULN persists for $\geq 2$ weeks ALT $\geq$ 3xULN but $<5$ xULN persists for $\geq 4$ weeks
Bilirubin	ALT $\geq$ 3xULN and bilirubin $\geq$ 2xULN ( $>35\%$ direct bilirubin)
INR^2	ALT $\geq$ 3xULN and INR $>1.5$ , if INR (International normalized ratio) measured
Cannot Monitor	ALT $\geq$ 5xULN but $<8$ xULN and cannot be monitored weekly for $\geq 2$ weeks ALT $\geq$ 3xULN but $<5$ xULN and cannot be monitored weekly for $\geq 4$ weeks

	weeks
Symptomatic	ALT $\geq$ 3xULN associated with symptoms (new or worsening) believed to be related to liver injury or hypersensitivity
Required Actions and Follow up Assessments following ANY Liver Stopping Event	
Actions	Follow Up Assessments

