
 
• Immediately discontinue study treatment
 
• Report the event to GSK within 24 hours
 
• Complete the liver event CRF and complete an SAE data collection tool if the event also meets the criteria for an SAE
 
• Perform liver event follow up assessments (see Follow Up Assessments )
 
• Monitor the participant until liver chemistries resolve, stabilize, or return to within baseline (see MONITORING below)
 
• Do not restart/rechallenge participant with study treatment unless allowed per protocol and GSK Medical Governance approval is granted
 
• If restart/rechallenge not allowed or not granted, permanently discontinue study treatment and may continue participant in the study for any protocol specified follow up assessments
 
 
MONITORING:
 
For bilirubin or INR criteria:
 
 
• Repeat liver chemistries (include ALT, AST, alkaline phosphatase, bilirubin) and perform liver event follow up assessments within 24 hrs
 
• Monitor participants twice weekly until liver chemistries resolve, stabilize or return to within baseline
 
• A specialist or hepatology consultation is recommended
 
 
For All other criteria:
	
 
• Viral hepatitis serology
 
• Obtain INR and recheck with each liver chemistry assessment until the transaminases values show downward trend
 
• Only in those with underlying chronic hepatitis B at study entry (identified by positive hepatitis B surface antigen) and quantitative hepatitis B DNA
 
• Blood sample for pharmacokinetic (PK) analysis, obtained within 72 hours after last dose
 
• Serum creatine phosphokinase (CPK) and lactate dehydrogenase (LDH).
 
• Fractionate bilirubin, if total bilirubin <math>\geq</math> 2xULN
 
• Obtain complete blood count with differential count of leukocytes to assess eosinophilia
 
• Record the appearance or worsening of clinical symptoms of liver injury, or hypersensitivity, on the AE report form
 
• Record use of concomitant medications on the concomitant medications report form including acetaminophen, herbal remedies, other over the counter medications.
 
• Record alcohol use on the liver event alcohol intake case report form
 
 
For bilirubin or INR criteria:
 
 
• Anti-nuclear antibody, anti-smooth muscle antibody, Type 1 anti-liver kidney microsomal antibodies, and quantitative total immunoglobulin G (IgG or gamma globulins).
 

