### Phase III-IV liver chemistry increased monitoring criteria with continued therapy

Liver Chemistry Increased Monitoring Criteria – Liver Monitoring Event	
Criteria	Actions

ALT <math>\geq</math>5xULN and <8xULN and bilirubin <2xULN without symptoms believed to be related to liver injury or hypersensitivity, and who can be monitored weekly for 2 weeks.
 
OR
 
ALT <math>\geq</math>3xULN and <5xULN and bilirubin <2xULN without symptoms believed to be related to liver injury or hypersensitivity, and who can be monitored weekly for 4 weeks.
	
 
Notify the GSK medical monitor within 24 hours of learning of the abnormality to discuss participant safety.
 
Participant can continue study treatment.
 
Participant must return weekly for repeat liver chemistries (ALT, AST, alkaline phosphatase, bilirubin) until they resolve, stabilise or return to within baseline.
 
If at any time participant meets the liver chemistry stopping criteria, proceed as described above.
 
If ALT decreases from ALT <math>\geq</math>5xULN and <8xULN to <math>\geq</math>3xULN but <5xULN, continue to monitor liver chemistries weekly.
 
If, after 4 weeks of monitoring, ALT <3xULN and bilirubin <2xULN, monitor participants twice monthly until liver chemistries normalize or return to within baseline.
 

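### Protocol 8.1.1 words a mandatory liver stop as optional, and the SAP's AE-withdrawal tables are narrower than protocol 10.3.2

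*Protocol*

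**What the plan says.** **Liver stop.** Protocol 8.1 states: "A subject must be withdrawn from study treatment if any of the following stopping criteria are met". It lists the liver criteria among them and sends the reader to 8.1.1 and Appendix 6. In Appendix 6, under "Required Actions and Follow up Assessments following ANY Liver Stopping Event", the first action is "Immediately discontinue study treatment". Section 8.1.1 is softer: "Discontinuation of study treatment for abnormal liver tests should be considered by the investigator when a participant meets one of the conditions" of the algorithm, or when the investigator thinks it best for the participant. For events that meet only the increased monitoring criteria, Appendix 6 says "Participant can continue study treatment".

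**AE summaries.** Protocol 10.3.2, under the primary endpoint, promises summary statistics for AEs that lead to discontinuation of treatment or of the study. SAP 8.2 plans the corresponding tables by system organ class (SOC) and preferred term (PT) for study withdrawal alone, and the titles of Tables 2.13 (interim) and 12.27 to 12.29 (final) say the same. The listing line in SAP 8.2 and Listings 21 and 64 cover both outcomes. SAP 2.1 states that nothing departs from the analysis planned in the protocol.

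**Study status after a treatment stop.** Protocol 8.1.3 says: "A subject who discontinues the study treatment must be withdrawn from the study". Appendix 6 says that where rechallenge is not allowed or not granted, the site is to "permanently discontinue study treatment and may continue participant in the study for any protocol specified follow up assessments". Section 8.1.4.1 bars rechallenge after a liver stop for everyone. Appendix 4 says: "Any female participant who becomes pregnant while participating will discontinue study treatment or be withdrawn from the study".

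**The concern.** A site that opens the section on liver stopping criteria finds a sentence that leaves the stop to judgement, while the two places around it give an order. A rule that protects participants should read the same way wherever it appears.

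The second point concerns how a primary-endpoint summary is defined. Stopping treatment because of an AE is a standard tolerability measure, and the protocol asks for it together with study withdrawal. A table restricted to study withdrawal can miss a participant who stopped treatment for an AE but was not recorded as leaving the study. The wording in Appendices 6 and 4 is the route by which that could happen. Table 2.13 also belongs to the Week 24 report intended for the Japanese submission.

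**Working it through.** **1. Liver rule, side by side.**

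| Participant meets | 8.1 | 8.1.1 | Appendix 6 |
|---|---|---|---|
| A stopping criterion (e.g. ALT at least 8×ULN) | must stop | stopping to be considered | stop immediately |
| Monitoring criteria only (e.g. ALT 3 to below 5×ULN, bilirubin below 2×ULN, no symptoms, weekly monitoring possible) | no stop required | stopping to be considered | may continue |

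The titles of Algorithms A and B show that the algorithm covers both rows, so the 8.1.1 sentence does too. It fits the second row and conflicts with the other two texts in the first.

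**2. What the tables count.** Let T be the participants with an AE that led to stopping treatment, and S those with an AE that led to study withdrawal.

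- Protocol 10.3.2 asks for T or S.
- SAP 8.2 and the four tables count S.
- The shortfall is the number in T but not in S.

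If 8.1.3 is followed and both records agree, everyone in T is also in S and the shortfall is zero. Under Appendix 6, a participant may stop treatment and stay in the study for follow-up. Because 8.1.4.1 bars rechallenge, that branch applies to every liver stop. Such a case enters T only if the liver finding is itself reported as an AE. The SAP lists reasons for study withdrawal and for treatment discontinuation separately (Listings 45 and 46), so the two records can differ.

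**3. Size.** Protocol 10.1 gives 110 enrolled and 100 completing. That is 110 − 100 = 10 drop-outs, or 10/110 = 9.1%, in line with its stated rate of approximately 10%. If all 110 are treated, the fall in the total column of Table 12.27 is:

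- 1 missed participant: 1/110 = 0.91 percentage points
- 2 missed (assumed): 2/110 = 1.82 points
- 3 missed (assumed): 3/110 = 2.73 points

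The SAP sets no allocation ratio. For assumed dose groups of 30, 55 or 80, one missed participant is 1/30 = 3.33, 1/55 = 1.82 or 1/80 = 1.25 points in that group's column. The documents give no rate for such cases.

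**4. Where a missed case would still show.** It would be in Listing 64, in the treatment-status summary with reasons (SAP 6.1.1, Table 11.2) and in overall AE incidence (Table 12.3). It may also be in the AE overview (Tables 2.2 and 12.2), but the rows of that shell are not given.

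**The case against.** **On the liver sentence.** It governs a mixed set. A blanket mandatory stop would contradict the Appendix 6 allowance for monitoring events, so soft wording is defensible for part of its scope. The algorithm figures cannot be seen and may carry a firm instruction. This explains the sentence, and it lowers confidence. It does not remove the conflict for stopping events, because the sentence makes no exception for them. A reader might infer that the protocol has no binding liver stop, or lets sites keep dosing after a stopping event. The documents do not support that: 8.1 and Appendix 6 both impose the stop, and 8.1.1 refers the reader to Appendix 6.

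**On the tables.** The AE overview may already count AEs leading to treatment discontinuation, and Table 11.2 gives the reasons for stopping treatment, with AE among the reasons captured in the CRF. A reader might infer that the promise in 10.3.2 is wholly unmet. That cannot be established. What is shown is that the SOC/PT tables are narrower than the protocol and than the SAP's own listings. Separate listings for the two statuses do not prove that the planners expected them to differ.

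**On study status.** A reader might infer that Appendices 6 and 4 must be rewritten to match 8.1.3. That does not follow. Section 8.1.3 stands under a heading about temporary discontinuation. Appendix 6 is permissive and limited to protocol-specified follow-up. In practice, either reading leads to the early withdrawal visit, the safety contact and the liver monitoring. Whether such a participant should be called withdrawn or retained is open to debate.

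**Conclusion.** Wrong as written, with low severity and moderate confidence. Two corrections are warranted: the 8.1.1 sentence for stopping events, and the definition of the AE-withdrawal tables in the SAP.

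The numerical effect on the tables is zero if every AE-led treatment stop is also recorded as a study withdrawal. Otherwise it is 0.91 points of the Table 12.27 total per missed participant, assuming that all 110 are treated. Any larger figure rests on assumed counts or group sizes. A reader might infer that AE withdrawals will be undercounted; the documents show only that they could be. No listed data would be lost, and overall AE incidence would not change.

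Confidence is held at moderate because the algorithm figures and the overview shell are unseen. The study-status wording in the appendices matters here only as the route by which the two AE sets can differ.

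**What to change.** **Protocol 8.1.1.** Replace the sentence with: *Study treatment must be discontinued when a participant meets any liver chemistry stopping criterion in Appendix 6. For a participant who meets only increased monitoring criteria, treatment can continue as in Appendix 6 unless the investigator judges that stopping is in the participant's best interest.*

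**SAP 8.2 and Tables 2.13 and 12.27 to 12.29.** Define and title them by either outcome, permanent discontinuation of study treatment or withdrawal from study, as the SAP 8.2 listing line and Listings 21 and 64 already do. SAP 2.1 then holds on this point. The definition is correct whichever way the study-status wording is read, so 8.1.3 and the two appendices need no change for this purpose.

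**Cost.** One protocol sentence, one SAP line and four table definitions. No new data are needed, because the reason for stopping treatment is already captured in the CRF (protocol 8.1) and listed.
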